8 PROTECTION OF HUMAN SUBJECTS

Prior to study initiation, appropriate approvals will be obtained from relevant authorities overseeing the study, e.g., Institutional Review Boards or Data Protection Agencies.

8.1 Informed Consent

Informed consent is not needed for this registry-based study, as there is no intervention or interaction with subjects, and subjects will not be identified.

PRODUCT: V501/V503	PROTOCOL/AMENDMENT VERSION NO.: V503-088-01-v1
REVOPS ID NO: NIS009722	CORE DRC APPROVAL DATE: 18JUL2024
EPIDEMIOLOGY NO.(PE STUDIES ONLY): EP08039.017	

9 MANAGEMENT AND REPORTING OF ADVERSE EVENTS/ADVERSE REACTIONS

Adverse Event (AE) and Product Quality Complaint (PQC) Reporting Language for Non-Interventional Study Protocols

Adverse Event and Product Quality Complaint Reporting

This is a non-interventional database study based on secondary use of data collected for other purposes. No administration of any therapeutic or prophylactic agent is required in this protocol. No reporting of individual adverse events or product quality complaints to regulatory agencies is planned for this database study because there is no access to individual patient/subject records, and it is not possible to assess the causality of individual cases. The investigator should refer to their institution's policy or local laws and regulations regarding reporting of any suspected adverse reactions and product quality complaints.

Any health outcomes (if collected per section 7.6.2), including any that qualify as adverse events, will be summarized as part of any interim analysis (including safety analysis, if required) and in the final study report, which will be provided to regulatory agencies by the Sponsor as required. Any relevant safety information will be summarized, and the Sponsor will include in the appropriate Periodic Safety Update Report (PSUR)/Periodic Benefit Risk Evaluation Report (PBRER) and/or Development Safety Update Reports (DSUR) if required.

PRODUCT: V501/V503	PROTOCOL/AMENDMENT VERSION NO.: V503-088-01-v1
REVOPS ID NO: NIS009722	CORE DRC APPROVAL DATE: 18JUL2024
EPIDEMIOLOGY NO.(PE STUDIES ONLY): EP08039.017	

10 PLANS FOR DISSEMINATING AND COMMUNICATING STUDY RESULTS

The primary results of this research study will be externally disseminated in a manuscript submitted to a peer-reviewed, scientific journal, abstract/presentation at a scientific conference or symposium, or results posted on the HMA-EMA Catalogue of Real-World Data. Any publication related to the study will need to be reviewed/approved by the Sponsor prior to submitting results externally. Any publication resulting from this work will adhere to the procedures and pre-specified analysis plans within this protocol.

PRODUCT: V501/V503	PROTOCOL/AMENDMENT VERSION NO.: V503-088-01-v1
REVOPS ID NO: NIS009722	CORE DRC APPROVAL DATE: 18JUL2024
EPIDEMIOLOGY NO.(PE STUDIES ONLY): EP08039.017	

REVOPS ID NO: NIS009722	CORE DRC APPROVAL DATE: 18JUL2024
EPIDEMIOLOGY NO.(PE STUDIES ONLY): EP08039.017	

12 ANNEXES

Annex 1 Graphical And Numerical Overview Of Potential Confounding In Assessment Of Hpv Vaccine Effectiveness Against Adult-Onset Rrp

Definitions:

Study exposure: HPV vaccination with GARDASIL or GARDASIL 9, below called HPV vaccination.

Study outcome: Adult-onset recurrent respiratory papillomatosis, below called RRP.

Primary objective: Estimate odds ratio (OR) of RRP (yes/no) given HPV vaccination (yes/no).

Power: The study has $\ge 80\%$ power to detect an OR of 3.0 with a lower bound of the 95% confidence interval of ≥ 1.33 , assuming at least 60 cases of AoRRP are observed.

Main association of interest:

The hypothesis is that HPV vaccination is negatively associated with the odds (likelihood) of RRP. Factors that may act as confounders to this association are considered, below. That is, factors associated with both exposure and outcome in such a way that an observed association between the two is partially or completely confounded.

Potential confounders:

Factors that are established to be associated with exposure/HPV vaccination in Nordic countries (Sweden, Denmark, and Norway):

1) Socioeconomic status:

In studies evaluating factors associated with uptake of HPV vaccination in the Nordic region, low education and low-income level of parent(s) were found to be associated with lower vaccine uptake [44][35]. Statistically significant associations (95% CIs excluded null) were observed when focusing on girls in the free of charge school-based program (hazard ratio [HR] or odds ratio [OR] estimates ranging from: 0.75 to 0.92 for low education and from 0.67 to 0.87 for low income in Denmark and Sweden, respectively) and the subsidized program in Sweden (HR=0.53 for low income and HR=0.32 for low education). Additionally, in Denmark, investigators assessed association between vaccine uptake and country of birth and found that uptake was significantly lower if born outside of Denmark (OR=0.49, 95% CI=0.42-0.57) [44]. Similarly, in Sweden, investigators assessed association between vaccine uptake and country of birth and found that uptake was significantly lower if born outside of Sweden (OR=0.49, 95% CI=0.48-0.50) [35].

PRODUCT: V501/V503	PROTOCOL/AMENDMENT VERSION NO.: V503-088-01-v1
REVOPS ID NO: NIS009722	CORE DRC APPROVAL DATE: 18JUL2024
EPIDEMIOLOGY NO.(PE STUDIES ONLY): EP08039.017	

2) Sexual behavior:

In a Swedish study examining acceptability of HPV vaccination in young adult women (up to age 30), investigators found that subjects with >1 sexual partner, a below median age of sexual debut, and defining themselves as bisexual were more willing to accept HPV vaccination than comparison groups. Effect sizes (ORs) were modest, ranging from 1.15 to 1.69, but statistically significant. Investigators also found that subjects who self-identified as being at high risk of a sexually transmitted infection (STI) were more willing to accept HPV vaccination (OR=2.0, 95% CI=1.56-2.17) [45].

It is difficult *a priori* to conclude that individuals with a previous history of STI may have an interest in vaccination against an STI. This case might be particularly existent for subjects with own, or maternal history of external genital warts, where the subject may then obtain vaccination against HPV/EGW which also incidentally protects against RRP. Therefore, there may be a positive association with previous sexual activity/previous EGW and likelihood of exposure in this study. However, the strength of the association is expected to be small-moderate.

In this context, it is important to note that a wide body of literature has addressed the possibility of riskier sexual behavior after HPV vaccination receipt. In this case, sexual habits could act as a mediator of the association between HPV vaccination and RRP and should not be adjusted for. However, no substantial evidence exists that suggests uptake of HPV vaccination leads to riskier sexual behavior, whereas on the contrary many studies have found no indications of change in behavior [46] [47] [48] [49] [50] [51] [52] [53].

3) Smoking:

There have been no comprehensive studies showing an association between smoking habits and willingness to vaccinate against HPV in the Nordic countries. An association between smoking and HPV vaccination can therefore be questioned.

Factors that are established to be associated with outcome/RRP diagnosis receipt in Nordic countries (Sweden, Denmark, and Norway):

There are no comprehensive local studies performed that analyzed risk factors for AoRRP due to rarity of the outcome. A recent international systematic review found that evidence about disease risk factors for RRP is limited but supported that the patient's smoking and sexual behavior are involved [54].

1) Sexual behavior:

The review concluded that "compared with disease-free controls, patients with RRP have a significantly higher median number of lifetime sexual partners" but also acknowledged that additional studies have mixed findings and conclusive evidence is lacking [54].

No large studies have been identified evaluating the association between sexual contacts and risk of RRP. A small study including 25 RRP patients [55], which is cited in the review by

PRODUCT: V501/V503	PROTOCOL/AMENDMENT VERSION NO.: V503-088-01-v1
REVOPS ID NO: NIS009722	CORE DRC APPROVAL DATE: 18JUL2024
EPIDEMIOLOGY NO.(PE STUDIES ONLY): EP08039.017	

Welschmeyer and Berke, reported an OR of 2.11 (95% CI=1.02-4.39) for RRP development in patients with more than 25 lifetime sexual partners versus in those with 0-5.

2) Smoking habits:

A study from 1989[56] is frequently cited as showing that smoking is a risk factor for RRP in adults. However, there are no robust statistical analyses presented in this report and more recent publications have not found an association with severity of disease. Yet, it remains a clinical observation that adult RRP patients tend to be smokers, and therefore, from a qualitative perspective, smoking may be considered potentially/somewhat associated with risk of RRP.

3) Socioeconomic status (SES):

While lower SES (of parents) has been found to be associated with risk of juvenile-onset RRP, to our knowledge, no studies exist confirming an association between SES and risk of RRP in adults (in Nordic countries or similar resource settings). One could speculate that subjects with higher SES may however be more prone to seek healthcare due to having a hoarse voice – the primary physical symptom in adult-onset RRP. However, it could be equally speculated that in a country with a strong tax-funded healthcare system, young women aged 15-29 years with a hoarse voice would be prone to seek healthcare attention regardless of social background, as the cost is very low to the individual whereas the social stigma would be equal. It could therefore be posited that SES be associated with risk of RRP through surveillance bias, but the strength of this association would be unknown.

Conclusions on potential confounders:

Although **socioeconomic status** appears to be moderately-strongly associated with exposure, there is no evidence suggesting it is associated with outcome. If there is an association with RRP as an outcome, it should be modest in size. However, in the interest of obtaining the best evidence, this association should be evaluated formally, and it is therefore planned to include this factor as a potential confounder in the analysis.

[figure not shown]
Regarding **sexual behavior**, the association with HPV vaccine exposure appears to be weak, whereas that with RRP (outcome) is stronger. This is expected given that causal HPV infection is acquired sexually. In Sweden, riskier sexual behavior was positively associated with willingness to be vaccinated, and therefore bias (due to this confounder) may be expected to be towards the null. Although number of sexual partners cannot explicitly be adjusted for in the proposed register-based study, age of vaccination will be accounted for in the analysis and minimal bias due to sexual behavior would be expected among those vaccinated at younger ages (<17 years), which is defined as exposure in the study primary analysis. Additionally, medical information regarding history of external genital warts (EGW) pre-vaccination may be obtained and used as a proxy for sexual behavior with particular relevance to risk of acquisition of low-risk types of HPV. EGW history is unique as the only STI where individual level register data is validated and available in all countries.

PRODUCT: V501/V503	PROTOCOL/AMENDMENT VERSION NO.: V503-088-01-v1
REVOPS ID NO: NIS009722	CORE DRC APPROVAL DATE: 18JUL2024
EPIDEMIOLOGY NO.(PE STUDIES ONLY): EP08039.017	

Finally, for **smoking habits**, the size of the association and thus potential for confounding due to this factor appears to be modest at most. Nordic registers cannot be used to define individual smoking status as this type of lifestyle factor is not systematically reported to national healthcare registries, especially not among subjects so young (in older age groups, there are proxy codes for smoking-related diagnoses and drugs that could be utilized but these are not relevant here). However, the inclusion of socioeconomic status is expected to serve as at least a partial proxy for smoking behavior, as previously used in HPV vaccine effectiveness studies [20]. It is believed that this approach adequately addresses potential confounding by this factor.

Annex 2 Table And Figure Shells For Rrp Study (Primary And Secondary Objectives)

Table 3 Number of new cases and incidence rates of recurrent respiratory papillomatosis, by calendar years (2000-2021)

G. A.		2000		2001				2002			2003			2004			2005		
Gender	No.	Inciden	ce Rate	No.		ice Rate													
and age	of	(per 10	00,000	of	(per 1	00,000	of	(per 10	00,000	of	(per 1	00,000	of	(per 10	00,000	of	(per 1	00,000	
group	cases	subj	ects)	cases	subj	00,000 ects)													
Women																			
All ages																			
0-14																			
15-29																			
0-4																			
5-9																			
10-14																			
15-19																			
20-24																			
25-29																			
0-16																			
17-29																			
Men																			
All ages																			
0-14																			
15-29																			
0-4																			
5-9																			
10-14																			
15-19																			
20-24																			
25-29																			
0-16																			
17-29																			

PRODUCT: V501/V503	PROTOCOL/AMENDMENT VERSION NO.: V503-088-01-v1
REVOPS ID NO: NIS009722	CORE DRC APPROVAL DATE: 18JUL2024
EPIDEMIOLOGY NO.(PE STUDIES ONLY): EP08039.017	

Table 3, continued.

Candan		2006		2007				2008			2009			2010		2011		
Gender	No.	Inciden	ce Rate	No.	Inciden	ice Rate												
and age	of		00,000	of		00,000	of	(per 10		of	(per 10		of		00,000	of		00,000
group	cases	subje	ects)	cases	subj	ects)												
Women																		
All ages																		
0-14																		
15-29																		
0-4																		
5-9																		
10-14																		
15-19																		
20-24																		
25-29																		
0-16																		
17-29																		
Men																		
All ages																		
0-14																		
15-29																		
0-4																		
5-9																		
10-14																		
15-19																		
20-24																		
25-29																		
0-16																		
17-29																		

PRODUCT: V501/V503	PROTOCOL/AMENDMENT VERSION NO.: V503-088-01-v1
REVOPS ID NO: NIS009722	CORE DRC APPROVAL DATE: 18JUL2024
EPIDEMIOLOGY NO.(PE STUDIES ONLY): EP08039.017	

Table 3, continued.

Candan		2012		2013			2014			2015			2016			2017		
Gender	No.	Inciden	ce Rate	No.	Inciden	ice Rate												
and age	of	(per 10	00,000	of	(per 10	00,000	of	(per 10	00,000	of	(per 1	00,000	of	(per 10	00,000	of	(per 10	00,000
group	cases	subj		cases		ects)	cases	subj		cases		ects)	cases	subj		cases	subj	ects)
Women																		
All ages																		
0-14																		
15-29																		
0-4																		
5-9																		
10-14																		
15-19																		
20-24																		
25-29																		
0-16																		
17-29																		
Men																		
All ages																		
0-14																		
15-29																		
0-4																		
5-9																		
10-14																		
15-19																		
20-24																		
25-29																		
0-16																		
17-29																		

PRODUCT: V501/V503	PROTOCOL/AMENDMENT VERSION NO.: V503-088-01-v1
REVOPS ID NO: NIS009722	CORE DRC APPROVAL DATE: 18JUL2024
EPIDEMIOLOGY NO.(PE STUDIES ONLY): EP08039.017	

Table 3, continued.

Candanandana	2018	2018				2020		2021			
Gender and age group	No. of	Incidence Rate	No. of	Incidence Ra		No. of cases	Incidence Rate		No. of		ce Rate
	cases	(per 100,000 subjects)	cases	(per 100,000 sub	(per 100,000 subjects)		(per 100,00	00 subjects)	cases	(per 100,00	00 subjects)
Women											
All ages											
0-14											
15-29											
0-4											
5-9											
10-14											
15-19											
20-24											
25-29											
0-16											
17-29											
Men		 									
All ages											
0-14											
15-29											
0-4											
5-9											
10-14											
15-19											
20-24											
25-29										ĺ	
0-16											
17-29											

[figure not shown]
Note: Age groups and calendar years may be combined if the number of cases in the cells is small.

Separate tables will be prepared for Sweden, Denmark, and Norway, and adapted to reflect the calendar years of coverage in those countries.

PRODUCT: V501/V503	PROTOCOL/AMENDMENT VERSION NO.: V503-088-01-v1
REVOPS ID NO: NIS009722	CORE DRC APPROVAL DATE: 18JUL2024
EPIDEMIOLOGY NO.(PE STUDIES ONLY): EP08039.017	

Figure 3 Overall age-adjusted and age-specific incidence rates of recurrent respiratory papillomatosis (RRP) among girls/women by year (2000-2021)

RRP in girls/women

[figure not shown]
Note: Calendar years may be combined if the number of cases in is small.

Separate figures will be prepared for Sweden, Denmark, and Norway, and adapted to reflect the calendar years of coverage in those countries.

PRODUCT: V501/V503	PROTOCOL/AMENDMENT VERSION NO.: V503-088-01-v1
REVOPS ID NO: NIS009722	CORE DRC APPROVAL DATE: 18JUL2024
EPIDEMIOLOGY NO.(PE STUDIES ONLY): EP08039.017	

Figure 4 Overall age-adjusted and age-specific incidence rates of recurrent respiratory papillomatosis (RRP) among boys/men by year (2000-2021)

Note: Calendar years may be combined if the number of cases in is small.

Separate figures will be prepared for Sweden, Denmark, and Norway, and adapted to reflect the calendar years of coverage in those countries.

PRODUCT: V501/V503	PROTOCOL/AMENDMENT VERSION NO.: V503-088-01-v1
REVOPS ID NO: NIS009722	CORE DRC APPROVAL DATE: 18JUL2024
EPIDEMIOLOGY NO.(PE STUDIES ONLY): EP08039.017	

Table 4 Characteristics of study population, AoRRP cases, and control subjects

	Study population,	AoRRP cases,	Controls,
	No. (%)	No. (%)	No. (%)
Total			
Age, years, mean (SD)			
Education level			
Low			
Medium			
High			
Missing			
Income level			
Low			
Medium			
High			
Missing			
Highest level of education			
achieved by mother*			
Low			
Medium			
High			
Missing			
Highest annual household			
family income level [‡]			
Low			
Medium			
High			
Missing			
Study Site			
Sweden			
Denmark			
Norway			
Country of birth			
Study site			
Other country			
Missing			
Own history of EGW			
Yes			
No			
Missing			
Maternal history of EGW			
Yes			
No			
Missing			
Length of follow-up in			
registries, years, mean (SD)			

AoRRP = adult-onset recurrent respiratory papillomatosis; EGW = external genital warts; SD = standard deviation

^{*}Education level of mother at index date.

[‡]Based on average level between 2006 (the start year of HPV vaccination) and the index date.

PRODUCT: V501/V503	PROTOCOL/AMENDMENT VERSION NO.: V503-088-01-v1
REVOPS ID NO: NIS009722	CORE DRC APPROVAL DATE: 18JUL2024
EPIDEMIOLOGY NO.(PE STUDIES ONLY): EP08039.017	

Table 5 Number of cases and odds ratio for recurrent respiratory papillomatosis (RRP) by HPV vaccination status

	AoRRP			
HPV vaccination	No. of cases ¹	No. of controls ²	Crude OR	Adjusted OR ³
status			(95% CI)	(95% CI)
Fully Vaccinated ⁴			Ref.	Ref.
Unvaccinated				

AoRRP = adult-onset recurrent respiratory papillomatosis; CI = confidence interval; HPV = human papillomavirus; ICD-10 = international classification of disease, 10^{th} modification; OR = odds ratio; Ref. = reference.

Notes on Table 5:

- 1. Separate tables will be prepared with outcome defined using: a) subcode D14.1.A, and b) code D14.1 and/or subcode D14.1A with at least one appropriate procedural code, i.e. DQB10 (Endoscopic extirpation), UDQ25 (Microlaryngoscopy with biopsy), and/or UDQ22 (Microlaryngoscopy).
- 2. Separate tables will be prepared considering: a) age at vaccination (≥17 years vs. any age at vaccination) and b) own history of external genital warts (yes/no).
- 3. Separate tables will be prepared with exposure defined as receiving at least one dose of Gardasil vaccine.
- 4. Separate tables will be prepared applying buffer period between vaccination and disease of 6 months (from last dose).
- 5. Separate tables will be prepared focusing on Gardasil use only as exposure.

¹ All study participants who acquired a first diagnosis of AoRRP as defined for each country.

² 10 controls matched on attained age, region of diagnosis and calendar year of case's diagnosis.

³ Adjustment factors considered for inclusion include education level, income level, country of birth, own history of external genital warts (EGW), and maternal history of EGW.

⁴ A female who received 3 doses (or 2 doses administered at 0 and 6-12 months if <15 years of age) of GARDASIL or GARDASIL 9 before age 17 will be classified as exposed and those who did not receive any dose will be considered unexposed.

PRODUCT: V501/V503	PROTOCOL/AMENDMENT VERSION NO.: V503-088-01-v1
REVOPS ID NO: NIS009722	CORE DRC APPROVAL DATE: 18JUL2024
EPIDEMIOLOGY NO.(PE STUDIES ONLY): EP08039.017	

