7.5 Stratification

Stratified analyses, statistical adjustment, and/or assessment of interaction will be performed for the primary objective according to the following factors:

- 1) Age at vaccination (girls/women vaccinated before 17 years of age or after 17 years of age compared to unvaccinated). Primary objective/analysis will focus on evaluation of vaccine effectiveness among females vaccinated before 17 years of age.
- 2) Personal history of external genital warts (yes/no).

PRODUCT: V501/V503	PROTOCOL/AMENDMENT VERSION NO.: V503-088-01-v1
REVOPS ID NO: NIS009722	CORE DRC APPROVAL DATE: 18JUL2024
EPIDEMIOLOGY NO.(PE STUDIES ONLY): EP08039.017	

Stratified analyses for the secondary objective will be performed according to calendar year, gender, and age.

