7.6.3 Covariates

In an observational study, where exposure is not randomized, it is important to explicitly express which association is being investigated, and a priori motivate which covariates are proposed for inclusion/exclusion and why. To this end, an Annex to this Protocol has been prepared which lists in detail subject matter expertise reasoning and motivation regarding potential confounders, specifically for the proposed association of study: potential effectiveness of HPV vaccination against AoRRP. Therein, a closer discussion on variables of consideration, the size of associations when known, and potential causal mechanisms supporting a confounding theory are discussed (Annex 1). For all covariates, missing data will be labeled as "Missing" and included as a separate category in the statistical analysis.

PRODUCT: V501/V503	PROTOCOL/AMENDMENT VERSION NO.: V503-088-01-v1
REVOPS ID NO: NIS009722	CORE DRC APPROVAL DATE: 18JUL2024
EPIDEMIOLOGY NO.(PE STUDIES ONLY): EP08039.017	

Covariates (potential confounders and/or effect modifiers):

- 1) Genital warts: External genital warts (EGW) or anogenital warts (AGWs) are, like RRP, caused by HPV6 and HPV11. History of EGWs is therefore expected to be a strong risk factor for RRP, with HPV6/11 infection being the likely causative agent for both conditions. It is important to consider that adjustment for EGWs may attenuate the estimated vaccine effect on RRP because some of the vaccine effect on RRP may be attributed to the EGW covariate. It is also possible that maternal history of EGWs may be associated with risk of AoRRP. An individual will be defined as having EGWs based on ≥1 hospitalization or outpatient record with diagnosis registered as A63 with subcodes, and/or a prescription for a pharmaceutical against anogenital warts (ATC codes D06BB10 [imiquimod] and/or D06BB04 [podophyllotoxin], as validated in Levàl et al, 2012 and Herweijer et al, 2014) [31] [34].

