Potential confounders such as highest level of family income and highest level of education achieved by the mother and/or subject income/education (tentatively in tertiles relative to the general age-matched population of the respective countries) will be adjusted for when investigating the primary objective, through inclusion in the conditional logistic regression. Given that most young adult females in their late teens/early 20s in Nordic countries have a similar level of education (i.e., almost all complete high school) and income is often limited due to being in school, adjustment for individual-level income and education will be considered and the decision of which variables to include in the model will depend on association of these variables with RRP outcome, and consideration of collinearity. Additionally, confounder assessment based on G-estimation may be undertaken if considered appropriate following discussion between the Sponsor and investigators.

Sensitivity analyses will be conducted in relation to the primary objective to assess the impact of: vaccine exposure definition (fully vaccinated versus ≥1 vaccine dose), age at

PRODUCT: V501/V503	PROTOCOL/AMENDMENT VERSION NO.: V503-088-01-v1
REVOPS ID NO: NIS009722	CORE DRC APPROVAL DATE: 18JUL2024
EPIDEMIOLOGY NO.(PE STUDIES ONLY): EP08039.017	

vaccination (any age and ≥17 years), applying buffer period between vaccination and disease onset of 6 months (from last dose), outcome definition (ICD-10 code D14.1 only versus cases [of D14.1] that have appropriate topography/morphology or SNOMED/Norpat codes, and cases [of D14.1] with at least one associated treatment/procedural code and/or specified with subcode D14.1.A/"larynx papilloma"), restricted to Gardasil use only (as exposure), and personal history of EGW (yes versus no). OR estimates from the regression model will be inspected in terms of point estimates and precision, for comparison with results from the main analysis. Effect size (OR) estimates are expected to vary across most sensitivity analyses. For example, effectiveness may be higher among females that are fully vaccinated, vaccinated at younger age (prior to sexual debut), without history of EGW, and in analyses including a buffer period and more restrictive outcome definition. For transparency, all preplanned analyses are described here.

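### Own genital-wart history has no time limit but may enter the primary adjusted OR; warts after vaccination result from the infection the vaccine prevents, so adjusting for them would pull the OR toward 1

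*Protocol*

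**What the plan says.** Own EGW history appears in several roles in the protocol.

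- **Annex 2, Table 5, footnote 3** (adjusted OR): the factors considered for inclusion are education, income, "country of birth, own history of external genital warts (EGW), and maternal history of EGW".
- **Section 7.5**: "Stratified analyses, statistical adjustment, and/or assessment of interaction will be performed for the primary objective according to the following factors". The second factor is "Personal history of external genital warts (yes/no").
- **Section 7.11**: income and education are the confounders named for adjustment. EGW stands at the end of the sensitivity list: "and personal history of EGW (yes versus no").
- **Section 7.6.3** (definition): "An individual will be defined as having EGWs based on ≥1 hospitalization or outpatient record with diagnosis registered as A63 with subcodes", and/or a wart prescription. No window relative to vaccination or index date is given. The same section says EGW, like RRP, is caused by HPV 6 and 11, and that "adjustment for EGWs may attenuate the estimated vaccine effect on RRP".
- **Annex 1, conclusions on confounders**: "medical information regarding history of external genital warts (EGW) pre-vaccination may be obtained and used as a proxy for sexual behavior". This is the only text that ties EGW to a time.
- **Annex 1, on sexual behavior**: if sexual habits changed after vaccination they could be a mediator, and then they should not be adjusted for.
- **Section 7.14** (general selection rule): factors associated with both exposure and outcome, examined by whether removal changes the width of the confidence interval by, for example, 10% or more.

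**The concern.** A wart record made after vaccination is not a baseline characteristic. It marks an HPV 6/11 infection, which is the event the vaccine is meant to prevent and the cause of the outcome. Section 7.8 cites Nordic estimates of 38% to 88% vaccine effectiveness against genital warts, so on the protocol's own evidence later EGW is affected by exposure. Conditioning on it removes part of the effect the primary objective is meant to estimate.

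Timing makes this the likely case. Primary exposure is full vaccination before 17, Section 5 puts median sexual debut at 16 to 17, and index age runs from 15 to 29. Most EGW on file by the index date can be expected to follow vaccination. It will not be all of it, since Section 5 also reports that 30% to 40% of 15-year-old girls are sexually active.

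At stake is the criterion in Section 7.8: an OR (unvaccinated versus vaccinated) of at least 3.0 with a lower 95% bound of at least 1.33. Attenuation works against both parts.

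**Working it through.** **1. The plan's own figure.** Inputs from Section 7.8: 60 cases, 10 controls per case, 25% coverage, true OR 3.0. Coverage odds in controls are 0.25/0.75 = 1/3. In cases they are 1/9, so case coverage is 0.10. Expected counts are 54 unvaccinated and 6 vaccinated cases, 450 and 150 controls.

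- SE(log OR) = √(1/54 + 1/6 + 1/450 + 1/150) = 0.441.
- Both criteria hold if log OR ≥ max(ln 3, ln 1.33 + 1.96 × 0.441) = max(1.099, 1.149) = 1.149.
- Chance of success = 1 − Φ((1.149 − 1.099)/0.441) = 0.455.

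Table 2 gives 0.80 for this cell. That matches a two-proportion test against OR = 1: Φ((0.15 − 1.96 × 0.0575)/0.0426) = 0.81. It does not match the stated lower bound of 1.33. The mismatch is a separate matter; here 0.455 is the baseline without EGW.

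**2. Adding any-time EGW.** Assumptions, none from the protocol except the 25% coverage: RRP arises only through HPV 6/11 infection; infection prevalence in the unvaccinated is 10% to 30%; the vaccine cuts infection to one third (so the true OR is 3.0); a share g of infected women have recorded EGW; 0% to 1% of uninfected women do; there is no confounding.

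One cell by hand, with prevalence 20%, g = 30% and background 0:

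| | Cases unvacc. | Cases vacc. | Controls unvacc. | Controls vacc. | OR |
|---|---|---|---|---|---|
| EGW no | 37.8 | 4.2 | 423 | 147 | 3.13 |
| EGW yes | 16.2 | 1.8 | 27 | 3 | 1.00 |
| All | 54 | 6 | 450 | 150 | 3.00 |

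The Mantel-Haenszel OR is (37.8×147/612 + 16.2×3/48)/(4.2×423/612 + 1.8×27/48) = 10.09/3.92 = 2.58. Unconditional logistic regression on the same expected counts gives 2.54 with SE 0.448. The success threshold becomes ln 1.33 + 1.96 × 0.448 = 1.163, and the chance is 1 − Φ((1.163 − 0.932)/0.448) = 0.30.

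The same calculation over the grid, true OR 3.0:

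| g | EGW-adjusted OR | Chance of meeting both criteria |
|---|---|---|
| no EGW in model | 3.00 | 0.455 |
| 10% | 2.85–2.93 | 0.41–0.43 |
| 30% | 2.54–2.67 | 0.30–0.34 |
| 50% | 2.19–2.35 | 0.19–0.23 |

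A second set of assumptions (prevalence 20% or 40%, RRP 100 times more frequent if infected) gives 2.85–2.87 at g = 10%, 2.35–2.42 at 40% and 1.97–2.04 at 60%.

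**3. Strata.** In the hand-worked cell the ORs by EGW are 3.13 and 1.00, although no effect modification was built in. Different stratum ORs would therefore be expected from conditioning on a consequence of infection alone.

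**4. The selection rule in Section 7.14.** Post-vaccination EGW is associated with both exposure and outcome, so it passes the first test. For g from 10% to 30%, adding it changes the log-scale interval width by 0.2% to 3.4%, and the OR-scale width by 1.5% to 13.5%. At 50% the OR-scale change is 16% to 24%. So the rule would often drop EGW, but on the OR scale it keeps it where the attenuation is largest. The section does not say which scale applies.

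**The case against.** The strongest reply is that no passage commits own EGW to the primary adjusted model. Footnote 3 says only that it is considered, Section 7.5 says and/or, and Section 7.11 names income and education for adjustment and puts EGW among the sensitivity analyses. Annex 1 already speaks of pre-vaccination EGW. The attenuation is disclosed, the crude OR is reported beside the adjusted one, and the bias is conservative. A look-back window is also often left to a statistical analysis plan.

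Much of this stands. A reader might infer that the plan requires adjustment for any-time EGW; it does not. A reader might also think the association-with-RRP rule in Section 7.11 would select EGW; that rule covers only individual income and education, and Section 7.14 rejects selection on outcome association alone.

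It does not close the point. The protocol gives a mediator principle and a pre-vaccination intent in Annex 1, and carries neither into the definition, Section 7.5 or Table 5. That is a conflict within the document rather than detail deferred. Disclosing attenuation does not decide whether EGW goes in. The crude-versus-adjusted comparison would not isolate it either, since income and education enter at the same step.

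The magnitude rests on undocumented inputs and assumes no confounding. Annex 1 expects confounding by sexual behavior to be toward the null, so EGW adjustment might offset some of it; but Annex 1 also expects that bias to be minimal for vaccination before 17.

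**Conclusion.** The point holds as a conditional one. The protocol leaves a post-exposure variable open for the primary adjusted OR, without a time limit and with a selection rule that cannot tell a confounder from a consequence of vaccination. If any-time EGW enters, the bias is toward the null: under the stated assumptions, a true OR of 3.0 becomes about 2.9 at 10% recorded EGW and 2.5 to 2.7 at 30%. The direction follows from the protocol's own account of EGW; the size depends on inputs it does not give.

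A reader might conclude that a true effect of 3.0 would be turned from success into failure. The figures do not support that. Success at a true OR of 3.0 is only about 45% likely without EGW, and falls to between 43% and 30% with it. Nor can this bias create a false success. The risk is an understated effect and a lower chance of meeting the criterion.

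**What to change.** State that own EGW is not in the primary adjusted model. Alternatively, admit it only as records before the first dose, with an equivalent reference age for unvaccinated women in the matched set. Carry the choice into Sections 7.5, 7.6.3 and 7.14 and Table 5 footnote 3, so that they agree with Annex 1. In Section 7.14, exclude variables that vaccination can affect before the interval-width test is applied. Report any-time EGW adjustment and EGW strata as labelled sensitivity analyses, with a note that differing stratum ORs are not evidence of effect modification.

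The cost is wording. EGW is still collected for the exploratory objective. The downside is slightly less control of confounding by sexual behavior, which Annex 1 expects to be minimal for vaccination before 17.
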